**[name]**

Associate Professor

Division of Biostatistics

College of Public Health

[name]

[[contact]](mailto:[contact])

disposable gloves, a dish sample collection device, and a mailed reminder. Both developed FIT outreach interventions will be compared to usual care (FIT, manufacturer's instructions).

Currently, FIT outreach programs are used in the United States. It is important to mail the FIT kits to patients without prior consent to reduce the selection bias that would occur if consent was obtained prior to the mailing. Patients will be mailed a notification letter one week prior to mailing the FIT kits and may contact the health center to opt out of future mailings.

## 2. SPECIFIC AIM

The specific aim for this study is to: **Conduct a pilot study of the two developed mail-based FIT outreach interventions vs. mailed usual care materials to establish acceptability and obtain preliminary efficacy data on increasing CRC screening.** Hypothesis A. FIT return and CRC screening process (primary outcome) will be higher among mid-life adults in both intervention groups (audio or video brochures) compared to those in the usual care group (*preliminary efficacy*). Hypothesis B. Mid-life adults in both intervention groups will have higher satisfaction with materials compared to those in the usual care group (*intervention acceptability*).

[figure not shown]
## 3. METHODS

### Pilot Study: Randomized Controlled Trial

#### Conceptual Model.

The intervention will be guided by the Protection Motivation Theory (PMT; Figure 2). Constructs include: intrinsic/extrinsic rewards of the maladaptive response (concerns about adverse events, negative social norms); severity/susceptibility (perceived CRC severity and vulnerability); response efficacy (FIT effectiveness); self-efficacy (confidence to complete FIT); and response costs (screening barriers). Fear is a mediating variable between severity and vulnerability and intention and focuses on CRC worry.

Figure 2. Protection Motivation Theory for FIT

#### Eligibility/ Recruitment.

A list of patients will be generated at the participating health system (COMPASS Community Health Center; letter of support Appendix A) of mid-life men and women (50-64 years old) who: 1) live in Appalachia; 2) had a medical visit in the past two years; 3) are at average-risk for CRC (no history of CRC, polyps, inflammatory bowel disease, family history of CRC or hereditary CRC syndromes); and 4) are not within CRC screening guidelines (no fecal occult blood test/FIT in the past year; flexible sigmoidoscopy in past five years; colonoscopy in past ten years). Only one person per household will be able to participate in the study to avoid any bias. The Compass Community Health Center will share patient names and addresses with [name] at OSU using secure email for all communication.

## Randomization.

The selected patients will be randomized to the: 1) usual care group; 2) audio brochure group; or 3) video brochure group. A random number generator will be used and a 1:2:2 allocation scheme (stratified by gender). We will continue until 160 patients have been randomized (Figure 3).

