### **Data Analysis.**

The specific aim of this proposal is to conduct a pilot study of the two developed mail-based FIT outreach interventions vs. mailed usual care materials to establish acceptability and obtain preliminary efficacy data on increasing CRC screening. Large sample sizes will not be required to achieve these goals. **Hypothesis A.** Mid-life adults in both intervention groups will have higher satisfaction with materials compared to those in the usual care group (*intervention acceptability*). Linear regression will be used to compare means and estimate differences (intent-to-treat analysis). These acceptability data will be critical to our subsequent application. **Hypothesis B.** FIT return (primary outcome) will be higher among mid-life adults in both intervention groups (audio or video brochures) compared to those in the usual care group (*preliminary efficacy*). We will randomize 64 patients in each intervention arm and 32 patients in the control arm (160 total, stratified for gender in each arm). This sample size will also allow us to characterize proportions +/-6% and means +/-0.13 standard deviation units in each intervention arm. We will estimate FIT return (primary outcome) using proportions for each study group. We assume

a return rate of 20% in control arm, 40% in audio brochure arm (OR=2.7), and 50% in video brochure arm (OR=4.0) based on the literature. Both comparisons (each intervention compared to control) will be a two-sample test of proportions (intent-to-treat analysis) using a one-sided alpha of 0.1 due to the preliminary nature of the study. With these assumptions, we have 96% power for the test of the video intervention and 77% power for the test of the audio intervention. We know that we will not be powered to detect small effect sizes or conduct sophisticated analyses (e.g. gender differences). We will estimate critical parameters with point estimates and 95% confidence intervals and provide a preliminary test of effectiveness on FIT completion. Results will provide preliminary data that will help power the future larger RCT. Data between the healthcare system and the OSU research team will be by secure encrypted email (Appendix O)

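### Does the 1:2:2 allocation, which makes the shared control arm the smallest, wrongly give away power?

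*Combined protocol and SAP*

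**What the plan says.** The Randomization section sets the ratio, "A random number generator will be used and a 1:2:2 allocation scheme (stratified by gender", and the total: "We will continue until 160 patients have been randomized". The Data Analysis section gives the matching arm sizes: "We will randomize 64 patients in each intervention arm and 32 patients in the control arm".

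The primary analysis is described as follows: "Both comparisons (each intervention compared to control) will be a two-sample test of proportions (intent-to-treat analysis", at a one-sided alpha of 0.1. The assumed rates are "a return rate of 20% in control arm, 40% in audio brochure arm (OR=2.7") and "50% in video brochure arm (OR=4.0) based on the literature". From these the plan concludes that "we have 96% power for the test of the video intervention and 77% power for the test of the audio intervention".

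Three other statements bear on the ratio:

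- The Specific Aim section gives the pilot two purposes, acceptability of the materials and preliminary efficacy.
- The Data Analysis section states the expected precision for each intervention arm, and says openly that small effects are out of reach.
- The Survey Non-Responders section says that what patients report will be used to revise the intervention before a later trial.

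The plan gives no explicit reason for choosing 1:2:2.

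**The concern.** When several treatments are compared with one control, the control arm enters every contrast. If those contrasts are the only goal, the control arm should be at least as large as each treatment arm. Here it is half as large. Both hypotheses, on FIT return and on satisfaction, compare each intervention with usual care, and no audio-versus-video test is planned. The 32 controls therefore limit every planned test.

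At stake would be about 7 points of power in the audio test, a wider interval for each difference from control, and a control return rate known less precisely than either intervention rate. The plan wants its results to help power a larger trial, and the control rate is a key input for that.

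**Working it through.** **Inputs** (Randomization and Data Analysis sections): 32 control, 64 audio and 64 video patients; return rates of 20%, 40% and 50%; one-sided alpha 0.1, so z = 1.2816. The alternative is the same 160 patients split 54/53/53.

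**Formula** (two-sample test of proportions, pooled variance under the null). With p̄ the weighted mean rate,

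SE0 = √[p̄(1 − p̄)(1/n_c + 1/n_t)], SE1 = √[p_c(1 − p_c)/n_c + p_t(1 − p_t)/n_t],

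power = Φ[(p_t − p_c − 1.2816·SE0)/SE1].

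**Step 1: the plan's own figures.**

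- Audio, 32 v 64: p̄ = 0.3333, SE0 = 0.1021, SE1 = 0.0935; (0.20 − 0.1308)/0.0935 = 0.740; power 77.0%. Stated: 77%.
- Video, 32 v 64: p̄ = 0.40, SE0 = 0.1061, SE1 = 0.0944; (0.30 − 0.1359)/0.0944 = 1.739; power 95.9%. Stated: 96%.

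Both reproduce, and 32 + 64 + 64 = 160 matches 1:2:2. Nothing is miscalculated or contradictory.

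**Step 2: equal allocation.**

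- Audio, 54 v 53: SE0 = 0.0885, SE1 = 0.0866; (0.20 − 0.1135)/0.0866 = 1.000; power 84.1%.
- Video, 54 v 53: SE0 = 0.0921, SE1 = 0.0876; (0.30 − 0.1181)/0.0876 = 2.076; power 98.1%.

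The audio gain of about 7 points is real. Exact enumeration of the same test gives 77.6% at 32 v 64 and 84.1% at 53 v 53.

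**Step 3: what each ratio does to precision.** 95% half-widths are 1.96 × SE with unpooled variances, in percentage points. The single intervention arm is taken at a 50% rate.

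| Quantity | 32/64/64 | 54/53/53 | Change |
|---|---|---|---|
| Audio minus control | 1.96√(0.16/32 + 0.24/64) = 18.33 | 1.96√(0.16/54 + 0.24/53) = 16.96 | −1.37 |
| Control rate (20%) | 1.96√(0.16/32) = 13.86 | 1.96√(0.16/54) = 10.67 | −3.19 |
| One intervention arm | 1.96√(0.25/64) = 12.25 | 1.96√(0.25/53) = 13.46 | +1.21 |
| Video minus audio | 1.96√(0.24/64 + 0.25/64) = 17.15 | 1.96√(0.24/53 + 0.25/53) = 18.85 | +1.70 |

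Equal allocation also gives 64 − 53 = 11 fewer users of each brochure.

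**Step 4: satisfaction.** The standard error of a difference in means, in SD units, is √(1/n_c + 1/n_t): 0.217 at 32 v 64 and 0.193 at 54 v 53 if every survey comes back. With the 85% return that the plan expects, dividing by √0.85 gives 0.235 and 0.210. The direction is the same and the difference is modest.

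**Step 5: timing.** The Survey Non-Responders section was written in response to a low return of surveys. Surveys travel in the kits mailed after randomisation, so some patients had already been randomised. The documents do not say whether randomisation was complete. If it was not, a new ratio would tie arm to calendar time, and the analysis would have to allow for that.

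**The case for a change.** The strongest case for the concern is that the plan never gives a reason for 1:2:2 and never sets the power cost against a benefit. Acceptability is itself framed as a comparison with usual care, so that contrast loses precision too. To reach 84% audio power at 1:2:2 would take about 200 patients (40 v 80 gives Φ(0.992) = 84.0%), so the ratio costs that one test the equivalent of about 40 patients. Intervention kits contain more items, so saving on kits cannot explain the choice. Finally, the quoted precision of ±6% and ±0.13 SD matches one standard error at n = 64 (√(0.25/64) = 6.25 points; 1/√64 = 0.125 SD). The 95% half-width of a proportion near 50% is about twice that, so the stated benefit of 64 per arm looks larger than it is.

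These facts all stand. They show that 1:2:2 is not the most efficient ratio for the two control contrasts, and that a sentence of justification would have helped the reader. They do not show that the ratio is wrong for this pilot. The rule that the control arm must be at least as large as the others holds only when control contrasts are the sole aim, and here they are not. How the precision is labelled is a separate matter: with correct labels, 64 per arm still estimates each new arm better than 53 does.

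**Conclusion.** The concern does not hold. The allocation, arm sizes and power statement are consistent, the plan's power figures reproduce to the rounding given, and the limited power is stated openly for a test that the plan itself calls preliminary.

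Putting more patients in the two new arms is a recognisable choice for a pilot that must also judge and revise its materials. The exchange is close. Equal allocation would add about 7 points of audio power and 2 points of video power, and would make the control rate clearly more precise. It would make each intervention-arm estimate and the comparison between brochures less precise, and fewer patients would try each brochure.

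This conclusion takes the plan's assumed return rates and alpha as given. It also reads the larger intervention arms as serving the acceptability and revision purposes; the plan's aims fit that reading, although it does not say so. The signs that kits had already been mailed make a change of ratio less practical, but the conclusion does not depend on that.

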## Intervention Groups.

The intervention groups will be sent (Table 1) a **Notification letter** (Appendix B) about the CRC screening study. If an individual opts out of participation in the study, their information will not be retained and their information will be deleted from the file by [name] when she is notified by the health center.

Approximately 7 days later, patients will be sent a kit that includes an **Information Sheet** (Appendix C) explaining the content of the kit and instructions on what to do depending on the group assignment.

**FIT.** The test and postage-paid return addressed envelope is included with the manufacturer's FIT instructions (Appendix D). An audio brochure or video brochure (described next) will be included in the kit. Participants only have to place their name, date of birth, and the date of their sample collection on the requisition form and the specimen collection bottle. They will be able to put the completed FIT in the mail using the return stamped addressed envelope.

[figure not shown]
**Audio Brochure or Video Brochure.** The audio brochure cover (Appendix E) and audio script (Appendix F) or video brochure cover (Appendix G) and video script (Appendix H) will provide targeted CRC screening information (6 minutes and 45 seconds) and will include FIT instructions (5 minutes and 30 seconds) in a format that will be engaging for individuals with limited health literacy. We enhanced the cultural appropriateness of the intervention by featuring pictures of individuals who look like adults from the Appalachian community and healthcare providers focusing on the CRC burden among Appalachian residents since targeted health information improves health outcomes. Due to COVID-19, we were not able to film the videos in Appalachia. We are using narrative over high quality photographs that were reviewed and chosen by community input (community members and healthcare providers). The intervention content targets PMT constructs (described in Conceptual Model section). We included testimonials for likeness between source and receiver; improving cultural similarity and message relevance.

**Disposable Gloves.** To address the screening barrier about the concern with the messiness associated with FIT completion, we will include disposable gloves that can be worn during specimen collection.

**Collection Device.** To assist with the collection of the stool sample, we are also including a dish collection device that makes it easier to collect a stool sample.

**Patient survey** (Appendix I: audio brochure group; Appendix J: video brochure group) and **Medical Record Release (MRR) form** (Appendix K) will be included in the kit with the FIT test. The survey assesses demographic characteristics (e.g. race, education, etc. and telephone number), PMT constructs (e.g. screening barriers), health literacy, perception of access to quality medical care, and satisfaction with educational materials using modified items from an existing satisfaction scale (Likert-type items). Patients will be asked to complete the survey even if they do not complete and return the FIT. Return of the survey will imply consent and participants will receive a \$25 gift card for

Figure 3. Pilot Test Overview and Intervention Components

completing the survey and a \$5 gift card for the return of the signed MRR (Appendix L). Gift cards will be mailed to participants within three business days after receipt of the signed documents. Participants will not have to answer any survey questions they do not want to answer. Participants will be allowed to return the FIT without the survey or MRR. We will call patients who return the survey to decrease missing data, if needed. Based on our previous research, we expect 85% will return the survey and 70% will return a MRR. We will include a stamped addressed return envelope so individuals may return the documents.

**Mailed Reminder (if necessary).** A mailed reminder (Appendix M) will be sent to participants who have not completed the FIT about two weeks after the initial FIT test mailing based on community input. Previous research has shown that FITs are usually returned within a few months. Participants may request a 2nd FIT if they misplaced the first FIT. The study's primary outcome is based on if an individual returns or does not complete the FIT test at two months.

Table 1. Components of Usual Care Group and Intervention Groups			
Component	Group(s)	Description	Theoretical Constructs
Notification Letter	All	• Recommendation for CRC screening	N/A
Patient Survey	All	• Demographic information • CRC screening history • FIT barriers/facilitators • Satisfaction with materials	• Severity, susceptibility • Rewards, response costs • Self-efficacy, Response-efficacy • Fear/worry
Medical Record Release	All	• Release of CRC screening results	N/A
FIT	Usual Care	• Manufacturing company FIT instructions	N/A
FIT	Audio	• Provides information about CRC screening • Brochure with targeted CRC information for residents of Appalachia, and testimonials • Provides step by step FIT audio instructions	• Severity, susceptibility, response efficacy • Rewards: Concerns and social norms • Fear/worry • Self-efficacy, response efficacy, response costs
FIT	Video	• Provides information about CRC screening • Brochure with targeted CRC information for residents of Appalachia, and testimonials • Provides step by step FIT visual and audio instructions	• Severity, susceptibility, response efficacy • Rewards: Concerns and social norms • Fear/worry • Self-efficacy, response efficacy, response costs
Disposable Gloves	Audio/Video	• Addresses a common patient barrier ("messiness")	• Response Costs
Dish Stool Collection Device	Audio/Video	• Addresses a common patient barrier (ease of collection)	• Response Costs
Screening reminders (if needed)	Audio/Video	• Mailed reminder about the importance of completing CRC screening (FIT)	• Rewards, response costs • Self-efficacy, Response-efficacy

### Usual Care Group.

The usual care group will be sent a **Notification letter**. This letter will be identical to intervention groups (Appendix B).

One week later patients will be sent a kit (Table 1) that includes an **Information Sheet** (Appendix C) explaining the content of the kit and instructions on what to do based on the group assignment.

**FIT.** The test and postage-paid addressed return envelope is included with the manufacturer's FIT instructions (Appendix D). Participants only have to place their name, date of birth, and the date of their sample collection on the requisition form and specimen collection bottle. They will be able to put the completed FIT in the mail using the return stamped addressed envelope. The FIT test will be sent

directly to the laboratory that works with the community health center. The FIT test will not be sent to OSU.

**Patient survey (Appendix N) and Medical Record Release (MRR) form (Appendix K).** The survey assesses demographic characteristics (e.g. race, education, etc. and telephone number), PMT constructs (e.g. screening barriers), health literacy, perception of access to quality medical care, and satisfaction with educational materials using modified items from an existing satisfaction scale (Likert-type items). Patients will be asked to complete the survey even if they do not complete and return the FIT. Return of the survey will imply consent and participants will receive a \$25 gift card for completing the survey and a \$5 gift card for the return of a signed MRR (Appendix L). Gift cards will be mailed to participants within three business days after receipt of the signed documents. Participants will be allowed to return the FIT without the survey or MRR. We will call patients who return the survey to decrease missing data, if needed. Based on our previous research, we expect 85% will return the survey and 70% will return a MRR. We will include a stamped addressed return envelope with the documents. Identical to intervention groups, participants may request a 2nd FIT if they misplaced the first FIT. The study's primary outcome is based on if an individual returns or does not complete the FIT test.

**Surveys.** The surveys will be designed using Teleform software by the Recruitment, Intervention and Survey Shared Resource (RISSR). This paper-based data collection software reduces error associated with data entry and directly inputs data into a database that is saved behind the OSU firewall.

### **Study Primary Outcome: FIT Return.**

FIT return at 2 months will be the primary outcome of this pilot study.

### **FIT Results and Follow-Up.**

The laboratory will send FIT results to the health center and participants will be notified of results per the health center's regular protocol. Participants with normal FITs will be mailed results including an explanation of the results and the importance of annual FIT completion. Participants with positive FITs will be called by the healthcare system to discuss results and will be referred for colonoscopy using current referral process. Participants with a positive FIT that cannot be reached by multiple attempts by telephone will be sent a letter instructing them to call the clinic for the FIT results. For participants who provide MRR, we will document FIT results. We will also document subsequent referral for colonoscopy, other CRC tests (e.g. colonoscopy) completed, and test results. [name] will assist with issues associated with follow-up of positive FIT that may arise during the study, if needed (all participants). If we do not have a signed MRR, the healthcare system will send us group data by study arm.

### **Data Analysis.**

The specific aim of this proposal is to conduct a pilot study of the two developed mail-based FIT outreach interventions vs. mailed usual care materials to establish acceptability and obtain preliminary efficacy data on increasing CRC screening. Large sample sizes will not be required to achieve these goals. **Hypothesis A.** Mid-life adults in both intervention groups will have higher satisfaction with materials compared to those in the usual care group (*intervention acceptability*). Linear regression will be used to compare means and estimate differences (intent-to-treat analysis). These acceptability data will be critical to our subsequent application. **Hypothesis B.** FIT return (primary outcome) will be higher among mid-life adults in both intervention groups (audio or video brochures) compared to those in the usual care group (*preliminary efficacy*). We will randomize 64 patients in each intervention arm and 32 patients in the control arm (160 total, stratified for gender in each arm). This sample size will also allow us to characterize proportions +/-6% and means +/-0.13 standard deviation units in each intervention arm. We will estimate FIT return (primary outcome) using proportions for each study group. We assume

a return rate of 20% in control arm, 40% in audio brochure arm (OR=2.7), and 50% in video brochure arm (OR=4.0) based on the literature. Both comparisons (each intervention compared to control) will be a two-sample test of proportions (intent-to-treat analysis) using a one-sided alpha of 0.1 due to the preliminary nature of the study. With these assumptions, we have 96% power for the test of the video intervention and 77% power for the test of the audio intervention. We know that we will not be powered to detect small effect sizes or conduct sophisticated analyses (e.g. gender differences). We will estimate critical parameters with point estimates and 95% confidence intervals and provide a preliminary test of effectiveness on FIT completion. Results will provide preliminary data that will help power the future larger RCT. Data between the healthcare system and the OSU research team will be by secure encrypted email (Appendix O)

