### **Survey Non-Responders.**

Due to the low return of completed surveys, an additional follow-up will be conducted. A letter from the health center participating in this study will be sent to patients who have not returned a completed survey and: a) who have not completed the FIT test (Appendix AA), or b) who have completed the FIT test. If a patient calls the toll-free number and is willing to complete the telephone interview, a script (Appendix CC) will be read prior to starting the interview that will include obtaining verbal consent for the telephone interview.

After verbal consent has been received, the interview will start. A few introductory questions and the interview guides (Appendix DD) are the approved surveys with a few less questions to decrease burden. The six different interview guides are based on what arm of the study (usual care, audio brochure, video brochure) the person was sent and whether they completed or did not complete the FIT test. Participants will be mailed the \$25 gift card if they complete the telephone interview. This additional opportunity to collect information from patients is important for revising the intervention prior to testing in a future trial.

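### The per-arm precision of ±6% and ±0.13 SD carries no confidence level and equals one standard error; the 95% intervals the plan will report are about twice as wide

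*Combined protocol and SAP*

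**What the plan says.** The Data Analysis section (section 3, Methods) plans 64 patients in each intervention arm and 32 in the control arm. It then says: "This sample size will also allow us to characterize proportions +/-6% and means +/-0.13 standard deviation units in each intervention arm". No confidence level is given, the figures are not called standard errors, and no other section defines them.

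The section goes on to assume FIT return of 20% in the control arm, 40% in the audio arm and 50% in the video arm. It gives power for one-sided tests at alpha 0.1 and then states how results will be reported: "We will estimate critical parameters with point estimates and 95% confidence intervals".

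Two other places bear on the means. The Patient survey paragraph under Intervention Groups says "we expect 85% will return the survey and 70% will return a MRR", and Usual Care Group repeats that expectation. Survey Non-Responders opens with "Due to the low return of completed surveys, an additional follow-up will be conducted" and gives no return rate.

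**The concern.** A ± figure offered as what a sample size can deliver is normally read as the margin of a confidence interval. The only confidence level the section names for its estimates is 95%. A reader who joins the two will expect 95% intervals of ±6 points and ±0.13 SD, which looks too narrow for 64 patients and a proportion near one half.

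This is the plan's only statement of per-arm precision. The trial is a pilot meant to supply estimates for powering a larger trial, so how well it can estimate return and satisfaction is part of the case for its size. At 40% return, the stated margin suggests an interval from 34% to 46%, whereas a 95% interval runs from about 28% to 52%.

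**Working it through.** **Inputs.** From Data Analysis: n = 64 per intervention arm, n = 32 in control, return of 40% (audio), 50% (video) and 20% (control), and 95% as the reporting level. From Intervention Groups: 85% survey return.

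**Step 1: reproduce the stated figures.** For a proportion SE = √(p(1−p)/n); for a mean in SD units SE = 1/√n.
- p = 0.4: √(0.24/64) = 0.0612
- p = 0.5: √(0.25/64) = 0.0625
- Mean: 1/√64 = 0.125 SD

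These round to 6% and 0.13, so both stated figures are reproduced as one standard error.

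**Step 2: see whether a usual confidence level gives them.** Half-width = z × SE at n = 64.

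| Level | z | p = 0.4 | p = 0.5 | Mean |
|---|---|---|---|---|
| 80% | 1.282 | 7.8 points | 8.0 points | 0.16 SD |
| 90% | 1.645 | 10.1 points | 10.3 points | 0.21 SD |
| 95% | 1.960 | 12.0 points | 12.2 points | 0.245 SD |

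None does. With the t distribution on 63 degrees of freedom the 95% half-width for a mean is 0.250 SD. Other 95% methods for the proportion, computed at 26/64 and 32/64, give similar widths: Wilson 11.7 to 11.9 points, Clopper-Pearson 12.6 to 12.8 points. Pooling both intervention arms (n = 128) still gives 8.7 points at p = 0.5 and 0.17 SD at 95%.

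**Step 3: the confidence the stated figures carry.**
- 0.06/0.0625 = 0.96 SE: 66.3%
- 0.06/0.0612 = 0.98 SE: 67.3%
- 0.13/0.125 = 1.04 SE: 70.2%

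**Step 4: the n that would give the stated figures at 95%.**
- ±6 points, p = 0.4: 0.24 × (1.96/0.06)² ≈ 256 per arm
- ±6 points, p = 0.5: 0.25 × (1.96/0.06)² ≈ 267 per arm
- ±0.13 SD: (1.96/0.13)² ≈ 228 per arm

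**Step 5: means with fewer surveys** (95%, t-based, per intervention arm).

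| Survey return | n | SE | 95% half-width |
|---|---|---|---|
| 100% | 64 | 0.125 SD | 0.25 SD |
| 85% (plan) | about 54 | 0.136 SD | 0.27 SD |
| 70% (assumed here) | about 45 | 0.149 SD | 0.30 SD |
| 50% (assumed here) | 32 | 0.177 SD | 0.36 SD |

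At the plan's own 85%, 0.13 SD is slightly optimistic even as one standard error. The protocol does not give the actual return, so the last two rows are illustrations only.

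**Step 6: control arm.** n = 32, p = 0.2: SE = √(0.16/32) = 0.0707, and 1.96 × 0.0707 = 0.139, about ±14 points.

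**Step 7: power.** A one-sided test at alpha 0.1 with 32 against 64 patients and pooled variance under the null gives 77.0% for 40% against 20% and 95.9% for 50% against 20%. The stated 77% and 96% are reproduced.

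**The case against.** The strongest reply is that nothing has been miscalculated. Both figures are correct as standard errors, estimate ± one standard error is a recognised convention, and the plan never calls them confidence limits. The sentence on 95% intervals stands apart from the precision sentence, and its reference to critical parameters is not defined. The sample size rests on a power statement that is reproduced, and a later trial would use the observed estimates and their reported intervals, not this planning sentence. Survey return is arguably a separate matter: the quoted sentence concerns the number randomized, and the telephone follow-up may recover some responses.

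Much of this stands. The figures reproduce, the link to 95% is the reader's inference, and no test or sample size depends on the sentence. But one standard error is a convention only when it is named, and 95% is the one confidence level the section gives for estimates. Survey return belongs here because the sentence covers means, satisfaction is measured by the survey, and the plan itself does not expect all 64 to return it. The 70% and 50% cases are assumptions and show no defect by themselves.

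**Conclusion.** The concern holds. The stated precision is one standard error without a label. At the plan's own reporting level the half-widths are 12.0 to 12.2 points instead of 6 (a ratio of 2.0) and about 0.25 SD instead of 0.13 (a ratio of 1.9). For satisfaction means the figure is about 0.27 SD at the planned survey return, and wider if fewer surveys come back.

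That the figures are standard errors is inferred from the arithmetic, since the plan does not say so; both match, and no usual confidence level does. The sizes rest on 64 per intervention arm and the assumed 40% and 50% return. The importance is modest: only the precision statement is affected. It should still be corrected, because it is the plan's sole account of what the pilot can estimate.

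**What to change.** Replace the sentence with wording such as: With 64 patients per intervention arm, 95% confidence interval half-widths are about ±12 percentage points for FIT return (at 40 to 50%) and about ±0.25 SD for means if all 64 return the survey; at the planned 85% survey return (about 54 per arm) the latter is about ±0.27 SD, and it widens further if fewer are returned.

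Optionally add about ±14 points for the 32 controls at 20% return. The minimum change is to keep the present figures and label them as standard errors, noting that the one for means assumes complete survey return.

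The cost is one sentence of protocol wording. It needs no extra patients and changes no test, analysis or power figure. The only drawback is that the stated precision looks less favourable.
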